Therapeutic plasma exchange followed by convalescent plasma transfusion in severe and critically ill COVID-19 patients: A single centre non-randomized controlled trial

trial registration number: NCT04973488

Date: 3 August, 2020

Study design, setting and population

A total of 38 Caucasian patients will be included in the present single center non-randomized controlled trial. All patients included in the study will be adults (>18 years) who present with acute respiratory failure and ARDS, and have positive reverse transcriptase-polymerase chain reaction (RT-PCR) test results for SARS-CoV-2 virus upon hospital admission. ARDS is defined as acute-onset hypoxemia (P/F ratio <300) with >50% bilateral pulmonary opacities on chest imaging within 24-48 h that are not fully explained by congestive heart failure and that require ICU treatment and monitoring. Exclusion criteria are represented by any of the following: Pregnancy, patients with suspected or confirmed pulmonary embolisms and patients with terminal disease, patients < 18 years of age. Patients enrolled in the study will be divided equally, non-randomized, into two groups as follows: A treatment group who will benefit of sequential TPE and CVP transfusion in addition to the standard treatment for COVID-19, and a control group who benefit of only standard treatment for COVID-19 (antiretrovirals, corticosteroids, anticoagulants and antibiotics if deemed necessary) according to hospital protocols. All patients will provide written informed consent immediately after admission into the ICU regarding all the procedures performed during hospitalization, including the treatment scheme applied in the present study and the use of the resulting data in scientific research publications, with the assurance that they will remain anonymous. In cases where obtaining informed consent from the patients will not be possible due to their critical medical condition, a legal representative will be informed and provide written consent. The trial was approved by the Ethics Committee of 'Pius Brinzeu' Emergency Clinical County Hospital Timisoara (approval no. 91/03.08.2020).

Study protocol

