The blood type of the patients will be determined immediately upon being admitted to the ICU. In the treatment group, a dual lumen, 14 French, dialysis catheter will be used for vascular access, by placing it in the femoral vein under echographic guidance. A single TPE session will be performed on the Infomed HF 440 machine (Infomed SA), with a plasma/blood separation ratio of 20%, using 40 ml/kg fresh frozen plasma as the substitute. The circuit will be anticoagulated with unfractionated heparin during the procedure. Upon completion of the TPE session, each patient from the treatment group will be transfused with 500 ml of ABO compatible CVP. Patients will be carefully monitored

during both the TPE session and the CVP transfusion, and also after the procedures, in order to treat emerging complications.

[figure not shown]

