Patients from the treatment and control groups will receive standard treatment for COVID-19 according to hospital protocols, consisting of corticosteroids, antiretrovirals, anticoagulants and antibiotics if deemed necessary. Patients from both groups will be anticoagulated with subcutaneous nadroparine (Fraxiparine; Aspen Pharma Trading) in therapeutic dosage, once every 12 h, adjusted according to bodyweight (≤ 70 kg: 3,800 Anti-Xa IU; >70 kg: 5,700 Anti-Xa IU). Patients from the treatment and control groups will receive corticosteroids in the form of 16 mg dexamethasone (Dexamethason; Krka) divided into 2 doses, daily. Antiretrovirals administered will be the ones in the hospital COVID-19 protocol lopinavir/ritonavir (Kaletra; Hetero Labs, Ltd.), 300 mg b.i.d. and remdesivir (Veklury; Gilead Sciences), 200 mg loading dose, then 100 mg o.d. for 5 days. Antimalarial drugs will also be used, in the form of hydroxychloroquine (Plaquenil; Sanofi-Aventis), 400 mg b.i.d. loading dose, then 200 mg b.i.d. Upon clinical (fever, chills, sweats or aspect/quantity of bronchial secretions) and paraclinical (leucocytosis, CRP or cultures) findings of infection, empiric antibiotics will be started, until de-escalation following culture results will be possible. Patients will be intensively monitored, and daily clinical and laboratory data will be collected during the ICU stay. Outcomes monitored will be survival at 30 days, oxygenation (P/F ratio) (normal ratio >300) and inflammatory markers [CRP (normal range 0-5 mg/l), LDH (normal range 135-225 U/l) and ferritin (normal range 30-400 μ g/l)] at the 7-day follow-up, as assessed using ASTRUP analyses and blood tests.

Statistical analysis plan

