Statistical data will be analysed using GraphPad Prism 8 (GraphPad Software, Inc.) and IBM SPSS Statistics 20 (IBM Corp.). The category variables will be characterized by value and percentage. Continuous variables will be presented as mean (\pm standard deviation) and median (interquartile range). Data distribution testing will be performed using the Shapiro-Wilk test. The numerical variables will be compared with the t-test for independent samples or the Mann-Whitney U test, depending on the type of distribution of the variables. The χ^2 test (or Fisher's exact test) will be used for the nominal variables. The Kaplan-Meyer method with the log-rank (Mantel-Cox) test will be applied to evaluate the primary endpoint. Cox regression will be utilized to determine hazard ratio of the treatment group. All statistical tests will be calculated with 2 tails and $P<0.05$ will be considered to indicate a statistically significant difference.

Local Ethics Committee Decision regarding Scientific Research in Human Subjects

SPITALUL CLINIC JUDEȚEAN DE URGENȚĂ „PIUS BRÎNZEU” TIMIȘOARA

• [name]
• Cod fiscal 4663448 • Telefon [name] • [contact]
• e-mail: [contact] • www.hosptm.ro

91/03.08.2020

DECIZIA COMISIEI LOCALE DE ETICA PENTRU CERCETARE STIINTIFICA A SPITALULUI CLINIC JUDETEAN DE URGENȚA TIMIȘOARA

Va comunicam avizarea din punct de vedere etic a studiului clinic cu titlul:

"Therapeutic plasma exchange succeeded by convalescent plasma transfusion in critically ill Covid -19 patients - a single center non- randomized controlled trial"

Departamentul in care se desfosoara: Compartiment ATI – Covid, Spitalul Clinic Judetean de Urgenta "Pius Brinzeu" Timisoara, Sectia ATI Covid, Spitalul Clinic Municipal Lugoj

Persoane responsabile pentru desfasurarea studiului clinic: Conducator de doctorat- [name]. [name], Laborator Clinic Central, doctorand- dr. [name], Clinica ATI - Spitalul Clinic Judetean de Urgenta "Pius Brinzeu" Timisoara.

Studiul se va realiza in baza consintamantului informat semnat de catre pacient/ reprezentant autorizat al pacientului la internarea in spital, consintamant care cuprinde si investigatiile imagistice care se efectueaza pe perioada internarii. Se va asigura anonimizarea totala a investigatiilor, pentru a nu permite sub nici o forma identificarea pacientilor.

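### Assignment is non-random with no stated rule or concealment, and the survival analysis is unadjusted, so confounding by prognosis cannot be excluded

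*Combined protocol and SAP*

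**What the plan says.** On size and assignment, the design section states "A total of 38 Caucasian patients will be included in the present single center non-randomized controlled trial" and then "Patients enrolled in the study will be divided equally, non-randomized, into two groups as follows". Nothing in the readable text says by what rule a patient goes to one group or the other, who applies it, or whether the next assignment is hidden from the person judging eligibility.

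The arms are visibly different. Under the study protocol heading: "In the treatment group, a dual lumen, 14 French, dialysis catheter will be used for vascular access", followed by plasma exchange and convalescent plasma. No sham or blinding is described.

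Consent is taken early: "All patients will provide written informed consent immediately after admission into the ICU regarding all the procedures performed during hospitalization, including the treatment scheme". A legal representative can consent instead.

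Eligibility covers a wide span of severity: "ARDS is defined as acute-onset hypoxemia (P/F ratio <300) with >50% bilateral pulmonary opacities on chest imaging within 24-48 h", with a need for ICU care.

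On analysis, "Outcomes monitored will be survival at 30 days" heads the outcome list. The statistical analysis plan applies Kaplan-Meier and the log-rank test to a primary endpoint that it does not name, but which the methods imply is survival. It adds: "Cox regression will be utilized to determine hazard ratio of the treatment group". It names no covariates, stratification, matching or propensity method.

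The ethics decision approves a study whose title also says non-randomized. It lists intensive care departments in two hospitals, Timisoara and Lugoj, although the trial is titled single-centre.

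**The concern.** The log-rank test and the hazard ratio will be read as the effect of plasma exchange plus convalescent plasma. That reading needs groups with comparable prognosis at the start. Random assignment would provide this on average, and concealment would protect it at enrolment. The plan has neither, and no baseline adjustment stands behind them. With 19 patients per group, a few placements related to prognosis could produce a sizeable apparent benefit or harm, and the reported analysis could not separate that from a treatment effect.

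The documents give no reason why randomization is impossible. Enrolment is prospective, the split is already equal, and consent to the study treatment scheme is already sought at ICU admission.

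**Working it through.** **Inputs from the documents.** 38 patients in two equal groups, so 38 / 2 = 19 per group; survival at 30 days; log-rank test, two-sided, 0.05. No power, effect size or mortality figure is given, so there is no stated calculation to reproduce.

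**Assumptions.** No treatment effect. Two prognostic classes with 30-day mortality of 30% (good) and 70% (poor). Exponential survival times, censored at day 30. Daily hazards are −ln(0.70)/30 = 0.0119 and −ln(0.30)/30 = 0.0401.

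**Step 1: spurious mortality difference.** If a share g of a group has good prognosis, its mortality is 0.30g + 0.70(1 − g) = 0.70 − 0.40g. The difference between groups is therefore 0.40 × (share in treated − share in control). For 60/40 this is 0.40 × 0.20 = 8 points.

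**Step 2: false-positive rate when the shares are probabilities.** Each patient's prognosis is drawn at random with the stated probability, so the actual counts vary between trials. Simulated log-rank, 20,000 trials per row:

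| Probability of good prognosis, treated/control | Spurious mortality difference | False-positive rate |
|---|---|---|
| 50/50 | 0 points | 5.2% |
| 60/40 | 8 points | 8.0% |
| 70/30 | 16 points | 17.1% |
| 80/20 | 24 points | 32.4% |

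**Step 3: false-positive rate when the counts are fixed.** The same test and hazards are used with exact good-prognosis counts. The approximate hazard ratio is ln(1 − treated mortality) / ln(1 − control mortality). For 13 v 6, treated mortality is (13 × 0.30 + 6 × 0.70)/19 = 42.6% and control mortality is (6 × 0.30 + 13 × 0.70)/19 = 57.4%. The ratio is ln(0.574)/ln(0.426) = 0.65.

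| Good-prognosis count, treated v control (of 19) | Mortality, treated v control | Approx. spurious HR | False-positive rate |
|---|---|---|---|
| 10 v 10 | 48.9% v 48.9% | 1.00 | 3.3% |
| 11 v 8 | 46.8% v 53.2% | 0.83 | about 5% |
| 12 v 7 | 44.7% v 55.3% | 0.74 | about 8% |
| 13 v 6 | 42.6% v 57.4% | 0.65 | about 13% |
| 15 v 4 | 38.4% v 61.6% | 0.51 | about 30% |

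The balanced row lies below 5% because fixing the counts removes chance variation in prognosis that the unadjusted test allows for.

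**Step 4: sensitivity.** With 20%/80% mortality instead, the fixed counts 11 v 8, 12 v 7, 13 v 6 and 15 v 4 give two-sided rates of 4.2%, 10.9%, 23.0% and 62.4%, and spurious hazard ratios of 0.76, 0.63, 0.52 and 0.35.

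**Step 5: how many patients this takes.** With 19 patients of each prognosis, the nearest to balance is 10 v 9. Reaching 13 v 6 takes three exchanges between groups (13 − 10 = 3), and 15 v 4 takes five. Steering sicker patients to treatment gives the mirror image, a spurious harm.

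**The case against.** The design is declared. Non-randomized appears in the title, in the text and in the title on the ethics decision, so nothing is hidden or contradictory. That stands: this is a design limitation. But the declaration does not supply an assignment rule, and it does not stop imbalance from entering the hazard ratio.

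A reader might infer that assignment is openly chosen, with the enroller setting each patient's group at the bedside. The documents do not support this. They do not say who assigns or how, and a figure not reproduced in the text could show patient flow. A rule based on hospital, calendar time or plasma availability would also fit the wording, and some such rules would leave the enroller no choice for a given patient. They would still be unconcealed or confounded, so the conclusion survives as a risk that cannot be excluded. It is not evidence that steering took place.

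A reader might also infer that any slight steering inflates the error rate. The fixed-count results do not show that: 11 v 8 stays at about the nominal 5%.

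There are also practical objections to randomizing. One stack of envelopes does not serve two hospitals, an ABO-compatible unit may not be available for every patient assigned to treatment, and a forced 19/19 list becomes predictable towards its end in an open trial. The first needs a central holder. The second is a reason to fix analysis by assigned group in advance. The third is limited: guessing from past assignments on one concealed list of 38 is right about [19 + (2^38/C(38,19) − 1)/2]/38 = 59% of the time, against 50% for a coin toss.

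**Conclusion.** The concern holds as a design weakness. The plan states non-random assignment with no rule, concealment or assigning role, the treatment is open, and the survival analysis is unadjusted. Followed exactly, it can give a confounded answer.

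Under the 30%/70% assumption, the two-sided false-positive rate is about 5%, 8%, 17% and 32% for good-prognosis probabilities of 50/50, 60/40, 70/30 and 80/20, or about 5%, 8%, 13% and 30% for fixed counts of 11 v 8, 12 v 7, 13 v 6 and 15 v 4. Small imbalance does little; moderate imbalance matters. The mortality rates and the imbalances are assumptions, since the documents give neither, and the direction of any bias cannot be known in advance.

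**What to change.** Before the first patient, replace the assignment sentence in the design section with 1:1 random assignment, 19 per group, from a computer-generated sequence. Someone who does not enrol or treat study patients should prepare it, and it should stay concealed until eligibility and consent are logged. If one site enrols, sealed, opaque, sequentially numbered envelopes are enough. If both hospitals named in the ethics decision enrol, use one central holder, for example by telephone. State in the statistical analysis plan that patients are compared by assigned group, and change the title and consent text to match.

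The cost is an ethics amendment or re-approval, since the study was approved as non-randomized and a notification alone is unlikely to suffice. Clinicians lose the choice of who gets plasma exchange, and some patients or representatives will decline. No patients, visits or procedures are added.

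If randomization is not accepted, state the assignment rule and who applies it, describe the survival comparison as an association and not a treatment effect, and adjust the Cox model for a baseline severity measure already collected, such as admission P/F ratio. At an assumed overall mortality of 50% there would be 38 × 0.5 = 19 deaths, so the model can carry very few covariates. Adjustment removes only measured confounding.

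### CRP, LDH and ferritin are compared at day 7 only, without baseline adjustment and with neither day 0 nor the exchange time fixed, although daily laboratory data are collected

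*Combined protocol and SAP*

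**What the plan says.** The Study protocol section gives the treatment group, and only that group, one plasma exchange "with a plasma/blood separation ratio of 20%, using 40 ml/kg fresh frozen plasma as the substitute". After it, "each patient from the treatment group will be transfused with 500 ml of ABO compatible CVP". Control patients have no plasma procedure.

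On data collection, the same section states: "Patients will be intensively monitored, and daily clinical and laboratory data will be collected during the ICU stay". The next sentence lists the outcomes: survival at 30 days, then P/F ratio, CRP, LDH and "ferritin (normal range 30-400 μ g/l)] at the 7-day follow-up, as assessed using ASTRUP analyses and blood tests". Day 7 is the only time named for the markers.

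The Statistical analysis plan compares numerical variables by t-test or Mann-Whitney U test, according to their distribution. It describes no baseline adjustment, change score or repeated-measures analysis. It assigns Kaplan-Meier and log-rank methods to the primary endpoint, which fits 30-day survival, so the markers appear to be secondary.

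On allocation, the Study design, setting and population section says: "Patients enrolled in the study will be divided equally, non-randomized, into two groups". The total is 38.

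The documents do not say when the exchange takes place, what day 7 is counted from, or whether a sample is taken just before the exchange.

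**The concern.** Three weaknesses meet in one comparison.

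- **Baseline.** Allocation is not random, so the groups may enter with different marker levels. An unadjusted day-7 test carries part of that difference into the result.
- **Timing.** The intervention is a single session. An effect that fades within days may be gone by day 7, and a null result could then be reported as no effect.
- **Removal.** The exchange acts on the compartment in which the markers are measured, in one group only. It can be expected to lower them at first even if inflammation is unchanged. How much of that remains at day 7 depends on when the exchange was done and how fast each marker recovers, and the plan fixes neither.

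At stake is the interpretation of the marker results. A lower value could be overread as control of inflammation, and a null could be overread as absence of effect.

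**Working it through.** The plan gives no power, effect size or SD for the markers, so there is no stated figure to reproduce. The calculations below are illustrations.

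**Inputs from the documents.** 38 patients divided equally, 38/2 = 19 per group; two-sided 5% level; one exchange of 40 ml/kg.

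**Assumed inputs.** Plasma volume 35 to 50 ml/kg; recovery half-lives of 1 to 5 days, not assigned to particular markers; equal correlation ρ between days; no missing values; normal approximation.

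**1. Precision and baseline.** Detectable difference at 80% power = (1.960 + 0.842) × √(2v/19), in SD units.
- Day 7 alone, v = 1: 0.91 SD (0.93 by the exact t-test).
- Day 7 adjusted for baseline, v = 1 − ρ²: 0.87, 0.79 and 0.65 SD at ρ = 0.3, 0.5 and 0.7.
- Mean of days 1-7 adjusted for baseline, v = (1 + 6ρ)/7 − ρ²: 0.51, 0.52 and 0.46 SD.

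Without adjustment, a baseline difference of δ SD shifts the expected day-7 difference by ρδ. At ρ = 0.5, that is half of whatever imbalance there was.

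**2. A short-lived effect.** Take an effect of 1 SD on day 1 that halves every h days. On day 7 it is 2^(−6/h). Power = Φ(effect × √(19/2)/√v − 1.96), counting only significance in the right direction, so the floor is 2.5%. For the 7-day mean, ρ = 0.5 gives v = (1 + 3)/7 − 0.25 = 0.321.

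| h (days) | Effect on day 7 (SD) | Power at day 7 | Mean effect, days 1-7 (SD) | Power, adjusted 7-day mean |
|---|---|---|---|---|
| 1 | 0.016 | 3% | 0.28 | 34% |
| 2 | 0.125 | 6% | 0.44 | 68% |
| 3 | 0.25 | 12% | 0.56 | 85% |

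The last column is power to detect a difference, not to attribute it, because early values also contain any removal.

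**3. Physical removal.** With perfect mixing and a marker confined to plasma, the fraction removed = 1 − exp(−40/PV). PV of 50, 45, 40 and 35 ml/kg gives 55%, 59%, 63% and 68%.

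With constant production, the deficit remaining t days later = fraction × 0.5^(t/half-life). Starting from 63%:

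| Days after exchange | Half-life 1 day | 2 days | 4 days |
|---|---|---|---|
| 2 | 16% | 32% | 45% |
| 4 | 4% | 16% | 32% |
| 7 | 0.5% | 6% | 19% |

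If day 7 fell only 3 days after the exchange, the deficit would run from 7-9% (half-life 1 day) to 36-45% (half-life 5 days), for removal of 55-68%.

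**4. Does the shape over time identify the cause?** Suppose 63% is removed, the half-life is 2 days and production falls permanently by 30%. The level just after exchange is 0.37 and the new steady level is 0.70, so level = 0.70 − 0.33 × 0.5^(t/2).
- Day 1: 0.70 − 0.23 = 0.47, a deficit of 53%.
- Day 7: 0.70 − 0.03 = 0.67, a deficit of 33%.

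The difference shrinks although the effect on production is real and sustained.

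**The case against.** The strongest counter-argument is that day 7 is a sensible time. Removal distorts the earliest values most and day 7 least, so a late reading guards against the very artefact at issue. This stands. A reader might infer that a day-7 value can never separate removal from an anti-inflammatory effect. The documents do not support that. They give no clearance figure, half-life or exchange time, and at assumed half-lives of 1 to 2 days only 0.5% to 6% is left a full 7 days later. The problem becomes material only for a slowly recovering marker, or if the exchange falls late in the window.

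A reader might also infer that daily values would settle the cause, with a shrinking difference read as removal and a persistent one as an effect on inflammation. That does not follow either. A genuine transient effect also shrinks, and step 4 of the working shows a sustained effect that both shrinks and persists.

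Two further objections are fair. The sentence on daily data does not name the three markers and covers only the ICU stay, so a full daily series cannot be taken for granted. The markers also appear secondary, and the plan states no mechanistic claim.

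None of this defends an unadjusted single-day test in a non-randomized trial, or leaves the day count defined.

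**Conclusion.** The point holds as a weakness in the analysis of apparently secondary outcomes. The firm part rests on the documents alone: one named time, an unadjusted test, non-random groups, an undefined day 0 and exchange time, and no planned use of the daily data.

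The low power for a fading effect (about 3% to 12%) is conditional on the assumed 1 SD starting size, the halving times of 1 to 3 days and complete data on 19 per group. Residual removal is a possibility of uncertain size. It is small for fast markers a full 7 days after exchange and about 19% at an assumed 4-day half-life. Baseline adjustment would deal with imbalance in the markers themselves, not with other differences between non-randomized groups.

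**What to change.** Change the Statistical analysis plan as follows.

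- Record the exchange time and count days from it; in controls, count from the matching ICU day, with the matching rule written down.
- Define baseline as the last value before the exchange, or the value on the matching day in controls.
- Analyse log CRP, log LDH and log ferritin over the available daily values to day 7 in a baseline-adjusted repeated-measures model with group, day and their interaction.
- Keep day 7 as the headline time and show the earlier group differences with confidence intervals. Report the early differences as not distinguishable from physical removal.
- State how death and ICU discharge before day 7 are handled, and give the number of patients contributing on each day by group.

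The cost is SAP wording and a modest amount of extra analysis. Two limits remain. The series will be incomplete after discharge or death, for reasons linked to outcome. The trial team must also confirm that the three markers are part of the daily laboratory data and that a pre-exchange value exists; if not, extra samples would be needed.

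### No rule for deaths before day 7: by default, P/F ratio, CRP, LDH and ferritin are compared only in patients who are alive and measured

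*Combined protocol and SAP*

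**What the plan says.** The Study protocol section lists the outcomes in one sentence. It begins "Outcomes monitored will be survival at 30 days" and goes on to P/F ratio, CRP, LDH and ferritin, which are taken "at the 7-day follow-up, as assessed using ASTRUP analyses and blood tests". The same section says that "daily clinical and laboratory data will be collected during the ICU stay".

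For analysis, the Statistical analysis plan states: "The numerical variables will be compared with the t-test for independent samples or the Mann-Whitney U test", the choice depending on distribution. Deaths are dealt with in one place only: "The Kaplan-Meyer method with the log-rank (Mantel-Cox) test will be applied to evaluate the primary endpoint". The primary endpoint is not named, but this method implies 30-day survival.

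The Study design, setting and population section restricts entry to patients with ARDS who "require ICU treatment and monitoring" and has them "divided equally, non-randomized, into two groups".

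Nothing in the documents says how a patient who dies before day 7 is handled in the four day-7 comparisons. There is no missing-data rule, last-value rule, rank or composite score, or defined analysis population.

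**The concern.** A t-test or Mann-Whitney test needs a value for each patient. The plan does not say that the dead are excluded, but unless a rule assigns them a value they drop out. The day-7 comparison then covers only patients alive and measured, and membership of that set can itself depend on treatment.

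If fewer treated than control patients die early, more of the sickest treated patients remain in the comparison, and a benefit on oxygenation or markers tends to be understated. If more treated patients die, it tends to be overstated. The bias is about zero only when each group loses the same share and the same kind of patient. That is not assured here: allocation is not randomized, and only one group receives a dialysis catheter, plasma exchange and plasma transfusion. This shows unequal exposure, not a known difference in mortality.

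Daily ICU values exist, so carrying the last value forward would also fit the text, as would ranking deaths worst. These analyses can give different answers, and nothing fixes the choice before results are seen.

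**Working it through.** The plan gives no day-7 mortality, SD, correlation, effect size or power, so there is no figure of its own to reproduce. The calculation shows how large the bias could be.

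**From the documents:** 38 patients divided equally, so 38/2 = 19 per group; two-sided 5% level; outcomes at day 7.

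**Assumed:** day-7 mortality of 5% to 30%; severity and day-7 P/F jointly normal with SD 1 and correlation ρ of 0.3 to 0.7; the share q with the worst severity dies before day 7.

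**Step 1: will it arise?** P(at least one death among 38) = 1 − (1 − p)^38. For p = 0.05 this is 0.858; for p = 0.10 it is 0.982.

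**Step 2: bias in survivors.** Losing the worst share q shifts the survivors' mean P/F by ρ·m(q), where m(q) = φ(z_q)/(1 − q):

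- m(0.10) = 0.1755/0.9 = 0.1950
- m(0.20) = 0.2800/0.8 = 0.3500
- m(0.30) = 0.3477/0.7 = 0.4967

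Bias, treated minus control, with no true effect = ρ_T·m(q_T) − ρ_C·m(q_C).

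| Deaths, treated vs control | ρ treated, ρ control | Bias in P/F (SD) |
|---|---|---|
| 10% vs 20% | 0.3, 0.3 | −0.046 |
| 10% vs 20% | 0.7, 0.7 | −0.108 |
| 10% vs 30% | 0.3, 0.3 | −0.091 |
| 10% vs 30% | 0.7, 0.7 | −0.211 |
| 20% vs 20% | 0.3, 0.7 | −0.140 |
| 20% vs 20% | 0, 0.7 | −0.245 |

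Swapping the groups reverses the sign. With equal deaths and a common ρ the bias is zero. For CRP, LDH and ferritin, where high is bad, the signs are mirrored.

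**Step 3: size against noise, and behaviour of the tests.** 10,000 simulated trials per scenario, 19 per group, Mann-Whitney test with tie correction. Measured means survivors only; worst rank means deaths tied at the worst value.

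| True effect | Deaths, treated vs control | ρ | Sampling SD of difference | Measured: rejects | Worst rank: rejects |
|---|---|---|---|---|---|
| 0 | 10% vs 20% | 0.3 | 0.351 | 5.3% | 6.7% |
| 0 | 10% vs 20% | 0.7 | 0.323 | 5.9% | 5.3% |
| 0 | 10% vs 30% | 0.3 | 0.364 | 5.3% | 13.9% |
| 0 | 10% vs 30% | 0.7 | 0.331 | 9.3% | 9.2% |
| 0.6 SD | 10% vs 20% | 0.3 | – | 30.8% | 39.7% |
| 0.6 SD | 10% vs 20% | 0.7 | – | 29.0% | 37.6% |
| 0.6 SD | 10% vs 30% | 0.3 | – | 25.1% | 53.1% |
| 0.6 SD | 10% vs 30% | 0.7 | – | 19.1% | 47.0% |
| 0.6 SD | 25% vs 25% | 0.3 | – | 32.2% | 16.3% |
| 0.6 SD | 25% vs 25% | 0.7 | – | 38.9% | 19.4% |

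Bias as a share of sampling SD: 0.046/0.351 = 13% to 0.108/0.323 = 33% at 10% vs 20%, and 0.091/0.364 = 25% to 0.211/0.331 = 64% at 10% vs 30%. In the latter case a true 0.6 SD appears on average as 0.505 (ρ = 0.3) or 0.388 (ρ = 0.7).

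**The case against.** The strongest reply is about weight. Every input is assumed. At 10% vs 20% deaths the type I error hardly moves, and the larger figures need about 2 versus 6 early deaths out of 19, or selection that differs sharply between groups. If fewer treated patients die, the planned test errs against treatment: at 10% vs 30% with no effect, false findings in favour of treatment occur in only 0.5% to 1.5% of simulated trials, against a nominal 2.5%. False benefit needs more treated deaths (4.4% to 8.2% at 30% vs 10%), and the survival curves would display that excess. Worst-rank analysis also does not remove the bias. It tests a different hypothesis, and one set of deaths would enter four correlated tests.

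Most of this stands, and it limits the point to a sensitivity analysis on outcomes other than survival. It does not make the gap harmless. Understating a real benefit is also an error, and survival curves do not show who contributed a day-7 value.

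Two related gaps are fairly raised. First, patients discharged from ICU before day 7, probably the healthier ones, may lack values. If the best share also goes unmeasured, then at 10% vs 30% deaths the bias is zero with discharges of 10% vs 30%, but −0.172 to −0.402 SD with discharges of 30% vs 10%. The follow-up may cover these patients, but the text does not say so. Second, the text does not say whether day 7 runs from ICU admission or from plasma exchange, which controls do not receive. Both need clarifying; neither removes the concern.

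**Conclusion.** The concern holds. The plan has no rule for deaths before day 7, and its named tests would by default compare only patients alive with a value. The resulting bias is small for modest differences in early mortality. It becomes material, up to about two thirds of the sampling SD, if early deaths differ as much as 10% vs 30% and severity strongly predicts the day-7 value. Equal death rates do not guarantee its absence if different kinds of patient die. These sizes rest wholly on assumed mortality and correlations; the omission itself is a matter of the text. Non-random selection into groups remains the larger threat to the trial, and this adds to it.

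**What to change.** In the Statistical analysis plan:

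- Keep the planned day-7 comparisons, but label them as conditional on being alive and measured at day 7.
- For each of the four outcomes, prespecify a sensitivity analysis: a Mann-Whitney test in which deaths before day 7 share the worst rank (lowest for P/F ratio, highest for CRP, LDH and ferritin), described as a combined comparison of death and marker.
- Report, per group, the numbers dead, discharged from ICU and measured at day 7, and how many living patients have no value. Interpret any day-7 difference only alongside these counts and the sensitivity result.
- State the starting point of day 7, and whether values are used for patients already out of ICU.

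The cost is wording. The test is already planned, and dates of death are needed anyway for 30-day survival. Only if the sponsor chooses to measure patients after ICU discharge might an extra blood gas sample be needed.

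The downside is that the worst-rank result partly repeats the survival analysis and loses about half the power when deaths are balanced (the 25% vs 25% rows in the table). It should therefore stand beside the measured-patient comparison and not replace it.
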